## 9 STATISTICAL CONSIDERATIONS

### 9.1 STATISTICAL HYPOTHESES

## Primary Hypotheses:

$H_1$ : Participants with an OUD are more likely to be engaged in MAT and/or non-pharmacological care for an OUD if the center is randomized to the CC vs the ECHO model of support.

$H_2$ : Participants with an OUD treated in CC centers are more likely to be retained in MAT and/or non-pharmacological care for an OUD than those treated in a center randomized to the ECHO model of care.

$H_3$ : Participants in the CC, compared to the ECHO condition, will have higher PAM scores at week 36 and 3-months post-partum.

## Secondary Hypotheses:

$H_1$ : Participants with an OUD are more likely to be engaged in MAT if the center is randomized to the CC vs the ECHO model of support.

$H_2$ : Participants with an OUD treated in CC centers are more likely to be retained in MAT for an OUD than those treated in a center randomized to the ECHO model of care.

$H_3$ : Babies born to mothers treated in CC centers will have higher birth weights on average compared to babies born to mothers treated in ECHO centers.

$H_4$ : Obstetrical providers randomized to the CC compared to the ECHO condition will score higher on subscales (autonomy, relationship with patients, patient care issues and relationship with staff) of the Physicians Worklife Survey.

$H_5$ : Participants in the CC, compared to the ECHO condition, are more likely to increase at least one PAM level from baseline to week 36 and 3-months post-partum.

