### **3 OBJECTIVES AND ENDPOINTS**

Our primary aims are:

- 1) To determine differences in **engagement and retention in OUD treatment** (MAT and/or non-pharmacological care) between participants who receive care from a center that uses a CC vs an ECHO support model. We hypothesize that the benefit from a CM and proactive monitoring approach will lead to greater treatment engagement and retention among patient participants.

H1a: Participants with an OUD are more likely to be *engaged* in OUD treatment if the center is randomized to the CC vs the ECHO model of support.

H1b: Participants with an OUD treated in CC centers are more likely to be *retained* OUD treatment than those treated in a center randomized to the ECHO model of care.

- 2) To determine differences in patient-reported outcomes between the two treatment models. For this domain we will use the **Patient Activation Measure (PAM)** as the sentinel measure. Patients can be assigned to one of four PAM levels based upon their scores. Originally, we planned to operationalize this outcome as whether or not patients increased at least one PAM level. Operationalization of this outcome was changed to a continuous outcome (i.e. the PAM score) on 10.25.21 to increase power for this outcome and to follow what is more commonly reported in the literature. The dichotomous outcome will be a secondary outcome.

H2: Participants in the CC, compared to the ECHO condition, will have higher PAM scores at week 36 and 3-months post-partum.

Our secondary aims are:

- 1) To determine differences in **engagement and retention in MAT** between participants who receive care from a center that uses a CC vs an ECHO support model. We hypothesize that the benefit from a CM and proactive monitoring approach will lead to greater MAT engagement and retention among patient participants.

H1a: Participants with an OUD are more likely to be *engaged* in **MAT** if the center is randomized to the CC vs the ECHO model of support.

H1b: Participants with an OUD treated in CC centers are more likely to be *retained* in MAT for an OUD than those treated in a center randomized to the ECHO model of care.

- 2) To determine differences in birth outcomes between participants who receive care from a center that uses a CC vs. and Echo support model. For this domain we will examine **birth weight**.

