H2: Babies born to mothers treated in CC centers will have higher birth weights on average compared to babies born to mothers treated in ECHO centers.

- 3) To determine differences in obstetrical providers' work satisfaction among the two treatment models according to the **Physicians Worklife Survey**.

H3: Obstetrical providers randomized to the CC compared to the ECHO condition will score higher on subscales (autonomy, relationship with patients, patient care issues and relationship with staff) of the Physicians Worklife Survey.

Primary, secondary and exploratory outcomes are listed in the table below:

Outcome	Type of Outcome	Assessment Tool	Assessment timepoints	Sample size
Treatment engagement	Primary	Medical records and study database	Prenatal treatment period	264

Treatment retention	Primary	Medical records and study database	Birth and 3-months post-partum	264
Patient Activation	Primary	Patient Activation Measure	Baseline, 26 weeks ,36 weeks and 3 months post-partum	264
#/% initiated onto MAT	Secondary	Medical records and study database	Prenatal treatment period	264
#/% retained on MAT	Secondary	Medical records and study database	Birth	TBD
Birth weight	Secondary	Medical records and study database	Birth	264
Physician Work Satisfaction	Secondary	Physician Work Life Survey	Before first participant enrollment and after last participant enrollment	12
#/% increasing at least one PAM level	Secondary	Patient Activation Measure	Week 36 and 3-months post-partum	264
#/% offered MAT	Exploratory	Medical records and study database	Prenatal treatment period	264
#/% continuing MAT at 3 months postpartum	Exploratory	Medical records and study database	3-months post-partum	TBD
#/% engaging in an opioid treatment program at 3 months post delivery	Exploratory	Medical Records and study database	3-months post-partum	264
#/% abstinent from illicit opioids or misuse or prescription opioids	Exploratory	a. TLFB b. Urine Drug screens	a. monthly b. each prenatal visit and birth and post birth	264
#/% with concurrent substance use	Exploratory	a. TLFB b. Urine Drug screens	a. monthly b. each prenatal visit and birth and post birth	264
Low birth weight	Exploratory	Medical records and study database	birth	264
Resuscitation at delivery	Exploratory	Medical records and study database	birth	264
Fetal demise	Exploratory	Medical records and study database	birth	264
Preterm birth	Exploratory	Medical records and study database	birth	264

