### 9.4 STATISTICAL ANALYSES

#### 9.4.1 GENERAL APPROACH

We will follow CONSORT guidelines, modified for cluster randomized trials, for reporting the trial ([www.consort-statement.org](http://www.consort-statement.org))(IR-5). Plans for data analysis will follow the major aims articulated above (IR-1) and the matched-pain cluster-randomized study design. We will examine the distribution of variables through descriptive statistics and graphical tools to verify that model assumptions are met to assess relationships between variables. Data analyses will use the intent-to-treat principle and we will attempt to follow all participants regardless of their retention to treatment. Dropouts (MD-3) and completers will be compared on baseline characteristics. Missingness (MD-2,4) will be examined for quantity, type (missing completely at random versus missing at random or not missing at random), and pattern (monotone, or non-monotone). If missing data are a significant issue, we will use sensitivity analyses (MD-4) and multiple

imputation methods that are appropriate for clustered data to fill in missing values in order to minimize bias, maximize available information and get accurate estimates of uncertainty. The possible impact of missing data on interpretation will be discussed in reports.

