#### 9.4.2 ANALYSIS OF THE PRIMARY ENDPOINT(S)

We updated our analysis plan on 1.30.24 since two sites recruited only one participant. We wanted to make use of the data from their matched pairs rather than having to drop 4 sites from our analyses. Thus, to increase the efficiency of our matched pair design and maximize data utilization from all sites we will not account for the matching of clusters in our analyses.

We will test differences between treatment groups in the proportion of participants who are engaged and retained in treatment using generalized linear mixed models (GLMM). GLMM models will include a random effect for site to account for potential positive correlations among observations within sites and will evaluate the fixed effect for the interventions. For the PAM outcome, we plan to conduct linear mixed models, where the response variable will be the PAM score at the week-36 assessment and at 3-months post-partum. Models will include a random effect for site and will evaluate fixed effects for the interventions and baseline PAM scores. If assumptions of normality are violated, we will consider transformations or alternative distributions to determine the model with the best fit. Due to the small number of samples, we will use small sample corrections in our mixed models. For continuous outcomes we will use Satterthwaite's degrees of freedom approximation given the small number of clusters and high variability in size of clusters in our study. For binary outcomes we will use restricted pseudo-likelihood with between-within correction to the degrees-of-freedom.

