#### 9.4.3 ANALYSIS OF THE SECONDARY ENDPOINT(S)

To tests differences in secondary patient outcomes between care models groups, we will use GLMM as described above.

Our co-Investigator, [name] will collect and analyze qualitative data. Qualitative interviews will be will be audio recorded, transcribed, and independently coded by two trained masters level researchers who will be supervised by [name]. All transcripts will be de-identified. The team will develop codes to be used in the content analysis(102, 103) and utilize these codes to identify themes related to deployment of the two models. Themes will be examined both within and across informant groups. The team will use NVivo (104) to analyze data. Subsequent to the initial training, two staff will independently code each transcript and meet together with [name] to compare codes, discuss and work towards consensus in order to build a common understanding and use of codes.(105) [name] will review interrater reliability on a regular basis in order to prevent coder drift and will retrain staff as needed. The collection of data from multiple informants, iterative process of data collection and analysis and use of two researchers to code transcripts, increases creditability, transferability, dependability, and confirmability of the findings.(105, 106)

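### The secondary outcome of rising at least one PAM level has no rule for women who start at the top level; read literally, they can never be responders

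*Combined protocol and SAP*

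**What the plan says.** Section 3 describes the scale: "Patients can be assigned to one of four PAM levels based upon their scores". It also records that the PAM outcome was changed on 10.25.21 from a level-based responder outcome to the continuous score, and adds: "The dichotomous outcome will be a secondary outcome". Secondary H5 in section 9.1 gives the responder definition, which is that women in CC "are more likely to increase at least one PAM level from baseline to week 36 and 3-months post-partum". The outcome table in section 3 lists it as secondary, at week 36 and 3 months post-partum, with 264 in the sample-size column.

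Section 9.4.1 says: "Data analyses will use the intent-to-treat principle", and section 9.3 repeats this for the primary analyses. Sections 5.1 and 5.2 contain no entry limit on PAM. For secondary patient outcomes, section 9.4.3 says only: "we will use GLMM as described above". What stands above it, in section 9.4.2, is a GLMM for engagement and retention with a random site effect and a fixed intervention effect. A linear mixed model for the PAM score follows, of which it says: "Models will include a random effect for site and will evaluate fixed effects for the interventions and baseline PAM scores".

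No section restricts the responder outcome to women at levels 1-3, counts holding level 4 as success, or mentions a ceiling.

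**The concern.** A woman at level 4 at baseline has no level above her, so she cannot meet the definition at either time point. She is then scored like a woman who falls from level 3 to level 1, although one has kept the best possible state and the other has worsened.

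Two consequences follow. First, women who cannot respond dilute any true difference between the arms. Second, if the arms differ in the share of women starting at level 4, the arm with more of them shows fewer responders with no treatment effect. Some imbalance by chance or selection is plausible. Clinics are randomised before women are enrolled (section 6.2.1), and the care manager enrols at CC sites (section 5.5). There are 12 clusters, and two sites recruited one participant each (section 9.4.2). The responder result could then appear to disagree with the primary continuous PAM result for reasons of scoring alone.

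**Working it through.** **Inputs from the documents (section 9.2).** CC responder rate 0.37, from 37% of 103 participants in another study; minimum detectable difference 0.20 and risk ratio 0.46 (Table 2), so ECHO 0.17; 6 matched pairs; 20 per site; CV k = 0.10; two-sided alpha 0.05; power 80%.

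**Input not in the documents.** The share q of women at level 4 at baseline. Assumed range 20% to 40%.

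**Formula.** Hayes-Bennett for matched pairs, with c pairs and n women per site:

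V = p1(1-p1)/n + p0(1-p0)/n + k²(p1² + p0²)

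power = Φ( √[(c-2)(p1-p0)²/V] - 1.96 )

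**Step 1. Reproduce the plan's figure.** With p1 = 0.37, p0 = 0.17, n = 20:

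- V = 0.01166 + 0.00706 + 0.00166 = 0.02037
- √(4 × 0.04 / 0.02037) = 2.803
- power = Φ(2.803 - 1.96) = 80.0%; risk ratio 0.17/0.37 = 0.46

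This matches the PAM row of Table 2. It does so at 20 per site, although the sentence introducing the table speaks of 40 per group. The text's other figure, a 15-point difference with 40 per site, gives 78.3% against the stated 80%. The formula has no term for women who cannot respond.

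**Step 2. Dilution with equal level-4 shares.** Suppose 0.37 and 0.17 are the rates among women able to rise. Counting everyone multiplies both rates by (1-q) with n = 20. Leaving level-4 women out keeps the rates but reduces n to 20(1-q).

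| q | Rates, all women | Difference | Power, all women | n per site, levels 1-3 | Power, levels 1-3 |
|---|---|---|---|---|---|
| 0 | 0.370 vs 0.170 | 0.20 | 80% | 20 | 80% |
| 0.20 | 0.296 vs 0.136 | 0.16 | 68% | 16 | 71% |
| 0.30 | 0.259 vs 0.119 | 0.14 | 61% | 14 | 66% |
| 0.40 | 0.222 vs 0.102 | 0.12 | 53% | 12 | 60% |

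Example for q = 0.20, all women: V = 0.01042 + 0.00588 + 0.00106 = 0.01736; √(4 × 0.0256 / 0.01736) = 2.429; power = Φ(0.469) = 68%.

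At each share, the restricted analysis has more power despite fewer women. These figures use the matched-pair formula of section 9.2. Section 9.4.2 has since dropped matching from the analysis, so they show relative loss and do not forecast the trial's actual power.

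**Step 3. Unequal level-4 shares, no true effect.** Take 0.37 in both arms among women able to rise.

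- Shares 20% and 30%: 0.37 × 0.80 = 0.296 and 0.37 × 0.70 = 0.259, a difference of 3.7 points.
- Shares 20% and 40%: 0.296 and 0.37 × 0.60 = 0.222, a difference of 7.4 points.

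With equal shares there is no false difference, only dilution.

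**The case against.** Four counter-arguments deserve weight.

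**The denominator.** A reader might infer from the outcome table that all 264 women are confirmed as the denominator and that level-4 women are expressly scored as failures. The documents do not go that far. The table lists 264 for the offer of MAT, for opioid abstinence and for engagement in an opioid treatment program at 3 months. Section 9.4.8 restricts the first two to women not in treatment at presentation and the third to women treated with MAT. The column mostly repeats planned enrolment. The point therefore rests on the definition, intention to treat and the absence of an exception.

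**Baseline adjustment.** A reader might infer that nothing in the plan adjusts for baseline. The reference in section 9.4.3 back to the models above could be taken to bring in baseline PAM. That is ambiguous, since the sentence on baseline PAM belongs to the linear models. Adjustment alone would not settle the matter anyway: a level-4 woman remains a certain non-responder whatever the covariates.

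**The planning rate.** A reader might infer that a planned 20-point difference must shrink to 12-16 points. Section 9.2 does not say that the 37% was confined to women below level 4. If it covered all comers, some ceiling is already in the rate and the loss in Step 2 is smaller or absent. This stands, and it makes Step 2 conditional.

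**Size and direction.** A reader might infer that the result will point the wrong way. The documents give no evidence of imbalance in level-4 shares, and 3.7 points is well below the 20-point detectable difference. The outcome is secondary, and the sponsor has already made the continuous, baseline-adjusted score primary. This limits the importance of the point but does not remove the gap in the definition.

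**Conclusion.** The concern holds as a flaw in the definition of a secondary outcome. On a four-level scale, with success defined only as a rise and no exception at the top, women who start at level 4 are non-responders by construction when the plan is read literally. Whether the binary model adjusts for baseline PAM is unclear.

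The size cannot be fixed from the documents. If the planning rates describe women able to rise, and 20-40% start at level 4, power falls from 80% to 68-53% with everyone counted, against 71-60% with those women left out. A false difference arises only if level-4 shares differ by arm; it is 3.7 points for 20% and 30%. The primary PAM conclusion does not depend on any of this. The change is worth making because it is cheap, but it is not critical to the trial.

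**What to change.** Before outcomes are analysed by arm, amend sections 9.1 and 9.4.3 and the outcome table as follows:

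- Analyse the PAM-level responder outcome among women at levels 1-3 at baseline, with baseline PAM as a fixed effect in the GLMM beside the intervention and the random site effect.
- As a supporting analysis in all women, count either a rise of at least one level or maintained level 4 as success.
- Report the present definition alongside, for continuity with the outcome as it stood before 10.25.21.
- Report the number and share of women at level 4 at baseline by arm, and change the table's 264 for this row to the restricted group.

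Baseline PAM is already collected (sections 1.3 and 8.1.1), so no new data are needed. The restriction uses a baseline variable, so it does not condition on anything that happens after enrolment. The costs are a somewhat smaller analysis set, a departure from the full intention-to-treat set for this one outcome, and a late change to a named secondary outcome, which should be dated and explained as the 1.30.24 update was.

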## 9.2 SAMPLE SIZE DETERMINATION

We plan to recruit a sample of 6 matched pair clusters (total of 12 clusters), with 6 clusters per condition and 20 patients per cluster for a total of 264 patients. Hypothesizing that CC will perform better than ECHO, this sample size achieves 80% power to detect a clinically meaningful minimum difference of 0.20 between the CC proportion (0.94) and the ECHO proportion (0.74).

To estimate the sample size needed to test differences between models of care in the proportion of women retained in treatment at delivery using a permutation test, we used the method of Hayes and Bennett (1999) for matched-pair cluster randomized trials. Our null hypothesis is  $p_{ECHO} = p_{CC}$  and the alternate hypothesis is  $p_{ECHO} \neq p_{CC}$ , where  $p$  is the proportion of women retained in treatment at delivery, setting a two-sided type 1 error rate of 0.05. We based the estimate of the proportion in the CC on a study by our co-investigator in which 94% of patients treated under a CC model continued MAT until delivery.

We could not find empirical data for an estimate of the coefficient of variation, so we followed the approach of Hayes and Bennett (1999). We generated 10,000 data sets with 6 clusters each, with true proportions assumed uniformly distributed between 0.72 and 0.99 to allow for a relatively wide range of plausible retention proportion values. In each of the simulated data sets coefficient of variation values were calculated based on formula (9) in the manuscript. This follows the conservative approach

suggested on p.322 of the paper (i.e. to use the coefficient of variation between clusters within each group as an upper limit for the coefficient of variation in matched pairs designs). After examining the distribution of the resulting coefficient of variation we selected 0.10 as the value for our subsequent power calculations since more than 90% of the data sets had values under that threshold.

In an ongoing study of mothers with depression randomized to cognitive behavioral therapy with or without a community ambassador, 37% of 103 participants increased by at least one PAM level. ([name], 2019, personal communication) Using this proportion for the CC group, 40 participants per site will provide 80% power to detect a 15% difference in the proportion of women who increase at least one PAM level between CC and ECHO. These estimates assume a two-sided test, with a significance level of 0.05 and an estimated within-pair coefficient of variation between clusters (CV) of 0.10.

For minimum detectable effect sizes for secondary outcomes at 80% power (assuming two-sided alpha = 0.05, 6 CC sites, 6 Echo sites, 40 participants per group, CV=0.1) we generated the table below.

Table 2 Continuous Outcomes	Mean (std. dev.) in Collaborative Care Group	Minimum detectable difference	Effect size (Cohen's d)
Birth weight	3137 (629)	597	0.95
Dichotomous Outcomes	Proportion for Collaborative Care Group	Minimum detectable difference	Effect size (Risk Ratio ECHO:CC)
Retained on MAT	0.89	0.20	0.78
PAM- increased 1 level*	0.37	0.20	0.46

We were not able to assess power for the remaining secondary outcomes: physician work-life survey and engagement with MAT given the limited prior research on these topics.

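### Section 9.2 claims 80% power for retention (0.94 vs 0.74) at 20 women per site, but the matched-pair method it names gives about 69%, and the section mixes 20 and 40 per site

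*Combined protocol and SAP*

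**What the plan says.** Section 9.2 describes a trial of 6 matched pairs, "with 6 clusters per condition and 20 patients per cluster for a total of 264 patients". It states that "this sample size achieves 80% power to detect a clinically meaningful minimum difference of 0.20 between the CC proportion (0.94") and 0.74 under ECHO. The calculation concerns "the proportion of women retained in treatment at delivery using a permutation test" and uses a published sample-size method for matched-pair cluster trials with two-sided alpha 0.05. For the CV, "we selected 0.10 as the value for our subsequent power calculations since more than 90% of the data sets had values under that threshold".

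The same section then says, for the proportion gaining at least one PAM level (0.37 under CC), that "40 participants per site will provide 80% power to detect a 15% difference", with "an estimated within-pair coefficient of variation between clusters (CV) of 0.10". Table 2 gives differences detectable with 80% power for secondary outcomes, assuming "6 CC sites, 6 Echo sites, 40 participants per group, CV=0.1": 597 g for birth weight, 0.20 for retention on MAT and 0.20 for the row "PAM- increased 1 level".

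Two other sections bear on this. Section 5.5 says the sample was reduced on 10.25.21 to 264 women, on average 20 per site after allowing for 10% attrition. Section 9.4.2 says that on 1.30.24 the matching was dropped from the analysis, because two sites had recruited one participant each. The analysis is now a mixed model with a random site effect.

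**The concern.** Section 9.2 gives every input to its retention calculation, so the stated power can be checked. Cutting the women per site from 40 to 20 must cost power, yet 80% is claimed for retention at 20 per site and for other outcomes at 40. For PAM level the section also gives two answers, 15 points in the text and 20 points in Table 2, from the same 0.37, CV and alpha, both labelled with 40 participants (per site in one place, per group in the other).

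Retention is a primary outcome. If its real power is well below 80%, a null result will be read as stronger evidence against a 0.20 difference than the design can supply. A reader also cannot tell which cluster size each figure in section 9.2 refers to.

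**Working it through.** **Inputs (section 9.2).** c = 6 pairs; m = 20 women per site; p1 = 0.94; p0 = 0.74; CV k = 0.10; z = 1.96 for two-sided alpha 0.05 and 0.8416 for 80% power. On attrition: 264 × 0.9 = 237.6, and 237.6/12 = 19.8, so 20 is the analysed number per site; 264/12 = 22 is the enrolled number.

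**Formula.** The documents name the method but do not print its formula. I use the standard form:

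- V = [p1(1−p1) + p0(1−p0)]/m + k²(p1² + p0²)
- clusters per arm for 80% power: c = a + (1.96 + 0.8416)² V/(p1−p0)², with a = 2 matched and a = 1 unmatched
- power with 6 per arm = Φ(√[(6−a)(p1−p0)²/V] − 1.96)

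For birth weight, V = 2 × 629²/m + k²(μ1² + μ0²).

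**Step 1. Does the formula reproduce the plan's own figures?** At 40 per site, matched:

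| Quantity | Printed | Matched, m = 40 | Unmatched, m = 40 |
|---|---|---|---|
| Birth weight, detectable difference | 597 g | 599 g | 540 g |
| Retained on MAT, detectable difference | 0.20 | 0.200 | 0.180 |
| PAM level (text), detectable difference | 0.15 | 0.153 | 0.138 |
| Retention 0.94 vs 0.74, power | 80% | 79.7% | 87.7% |

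The matched formula at 40 per site fits these printed figures. The unmatched one does not.

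**Step 2. Retention at the stated 20 per site.**

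V = (0.0564 + 0.1924)/20 + 0.01 × (0.8836 + 0.5476) = 0.01244 + 0.014312 = 0.026752

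Power = Φ(√(4 × 0.04/0.026752) − 1.96) = Φ(0.486) = **68.6%**

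Pairs needed for 80% = 2 + 7.849 × 0.026752/0.04 = **7.25**, against 6 planned.

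| Women per site | V | Power, matched | Difference with 80% power, matched | Power, unmatched, equal sites |
|---|---|---|---|---|
| 19.8 | 0.026878 | 68.4% | – | – |
| 20 | 0.026752 | 68.6% | 0.230 | 78.1% |
| 22 | 0.025621 | 70.5% | 0.225 | 79.8% |
| 40 | 0.020532 | 79.7% | 0.201 | 87.7% |

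With 6 pairs, the smallest site size giving 80% for 0.94 vs 0.74 is 41.

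**Step 3. The other figures at 20 per site (matched).**

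- PAM level, 15 points (0.37 vs 0.22): 52% at 20 per site, 78% at 40.
- PAM level, 20 points (0.37 vs 0.17): 80% at 20 per site, 97% at 40. The detectable difference is 0.200 at 20 and 0.153 at 40, so the PAM row of Table 2 fits 20 per site while the other two rows fit 40.
- Retained on MAT: detectable difference 0.236 at 20 (printed 0.20).
- Birth weight: detectable difference 628 g at 20 (printed 597 g).

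Taken literally, 40 per group is 40/6 = 6.7 per site. That would give 734 g, 0.35 and 0.30, which matches no row.

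**Step 4. Sensitivity to CV (matched, 20 per site).** Power is 81.8% at CV 0.07, 77.7% at 0.08, 68.6% at 0.10 and 59.5% at 0.12.

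**The case against.** The strongest reply is that 69% belongs to an analysis that will not be run. Section 9.4.2 ignores the matching, and the unmatched formula gives 78.1% at 20 per site and 79.8% at 22, close to the stated 80%. This is correct as arithmetic, but it does not support the text. Section 9.2 names the matched-pair method and argues its CV from matched designs. Matching was dropped more than two years after the sample was cut. The unmatched formula does not fit Table 2. It also assumes 12 equal sites, which section 9.4.2 shows is not the case. If the sponsor did use it, section 9.2 names the wrong method. What stands is that 69% must not be presented as the power of the planned mixed model.

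Second, CV 0.10 was chosen as a conservative upper limit, and matched power reaches 80% at a CV of about 0.075 with 20 per site. This too is correct, and it means the true power could be higher. But section 9.2 attaches its 80% to CV 0.10, so a smaller CV cannot justify the printed number.

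Third, the PAM row of Table 2 carries an asterisk whose footnote does not appear in the text available to me. It may have stated a different basis, such as 20 per site. The 15-point sentence may also be left over from when PAM level was a primary outcome; section 3 now lists it as secondary. So the PAM mismatch may be stale or unexplained text rather than a second miscalculation. The per-group label is probably a slip for per site. Both still need correcting.

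Finally, no estimate, test or interval changes, since the correction is to wording. That limits the cost of the fix. It does not make the stated power right.

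**Conclusion.** The concern holds. On the method and inputs stated in section 9.2, power for 0.94 vs 0.74 is 68.6% at 20 women per site and 70.5% at 22, about 10 to 11 points below the claim. The type II error is about 31% rather than 20%, and 80% power applies to a difference of about 0.23 (0.225 if all 264 women are counted). The likeliest explanation is a figure carried over from 40 per site, where the same formula gives 79.7%.

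This rests on the standard matched-pair formula, CV 0.10 and equal site sizes. The formula is supported by its agreement with the section's other figures at 40 per site. The conclusion does not depend on how attrition is handled. The power of the analysis now planned (unmatched, with very unequal sites) cannot be computed from the documents, because they do not give the full set of site sizes. The equal-site figures of 78.1% and 79.8% are optimistic for it.

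The mixing of 20 per site, 40 per site and 40 per group is a plain inconsistency that needs no formula to see.

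**What to change.** Restate section 9.2 on one formula and one cluster size, with a dated note of the change. Under the matched-pair method, suggested wording is:

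> With 6 matched pairs, 20 analysed women per site (264 enrolled, 10% attrition), CV 0.10 and two-sided alpha 0.05, power is about 69% for retention of 0.94 vs 0.74, and 80% for a difference of about 0.23.

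In the same revision:

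- Restate PAM level as 52% power for 15 points and 80% for 20 points.
- Restate Table 2 at 20 per site: about 628 g for birth weight, 0.24 for retention on MAT and 0.20 for PAM level.
- Correct both references to 40 participants, and state what the asterisk on the PAM row means.
- Remove the permutation test as the current test, since section 9.4.2 no longer uses it. The dated note can record it as the original planning basis.
- Add the power of the planned unmatched mixed model, computed by the sponsor from the actual site sizes under the planning assumptions (0.94 vs 0.74, CV 0.10) and not from observed results.

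One query, not an error: please re-check the statement that more than 90% of simulated CVs fell under 0.10. The plain SD/mean of six proportions drawn uniformly from 0.72 to 0.99 is under 0.10 in 68% of sets (83% with divisor n). The CV formula actually used is cited but not reproduced, so the two may differ.

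The cost is protocol/SAP wording and one power run. Enrolment, endpoints and analysis do not change; the stated power becomes less favourable.
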